#### 4.4.2.3.2 Supportive Analyses

As a sensitivity analysis, the change from Baseline in VAS (mm) at Week 6 and Week 12 will be compared between study products (test toothpaste vs. negative control and positive control vs. negative control) using the same ANCOVA models as mentioned in Section 4.4.2.2.2 but with Baseline VAS (mm) as a covariate, rather than the Baseline tactile threshold (g).

Using the above models, adjusted mean change from Baseline, along with 95% CIs will be reported by study product. P-values testing for non-zero change from Baseline will be presented for all study products. Mean difference between study products, 95% CIs and p-values will be provided for VAS (mm) score in Table 14.2.4.1.3. Significance testing will be conducted at the two-sided 5% significance level.

#### 4.4.3 Handling of Missing Values/Censoring/Discontinuations

Missing data will not be replaced or imputed. Subjects who withdraw from the study prematurely will be included in the statistical analyses up to the point of discontinuation.

MMRM analyses account for missing data using 'a missing at random' assumption, i.e., there is a systematic relationship between the propensity for missing values and the observed data, but not the missing data. Under such assumptions, MMRM is shown to provide unbiased estimates of the treatment effect, whilst the analysis of only complete cases using ANCOVA are biased (Baron et al, 2008; Ashbeck et al, 2016). Such complete case analysis requires a 'missing completely at random' assumption to remain unbiased and this is unlikely to hold, i.e., the fact that the data are missing is independent of the observed and unobserved data.

Using an MMRM, it will therefore be assumed that a subject with missing data at one post-Baseline visit would have obtained a similar efficacy result at that visit compared to a subject using the same study product with similar non-missing results at other timepoints (Baseline and the other post-Baseline visit).

Sensitivity analyses will present results from the separate ANCOVA models using only nonmissing values at each single time point. Additional sensitivity analyses may be added to the SAP prior to unblinding in case of high drop-out rates and/or exclusion from PP population.

#### 4.4.4 Pharmacokinetic (Secondary)

Not applicable.

## 4.5 Analysis of Safety

All safety data will be reported for the Safety Population as per actual study product received. No treatment kit list is generated for this study; unblinded site monitors will review the kits dispensed to subjects against the randomized treatment, and protocol deviations will be recorded in the event of a dispensing error. Therefore, the actual study product received will be assumed to be the same as the randomized treatment unless a protocol deviation is recorded to indicate that incorrect treatment was dispensed to the subject.

#### 4.5.1 Adverse Events and Serious Adverse Events

All AEs will be reviewed by the Clinical Research Scientist or Designee prior to database lock and unblinding, and will be coded to a system organ class (SOC) and preferred term (PT) using the Medical Dictionary for Regulatory Activities (MedDRA).

AEs will be classified as oral and non-oral on the AE page of eCRF.

Treatment emergent adverse events (TEAEs) are defined as new AEs that occur on or after the first study product use at Baseline (Visit 2; if this date is missing, a suitable alternative will be used, e.g., date of randomization). AEs with an onset date/time prior to the first study product usage will be considered as non-treatment emergent. In case of misallocation, compared to the randomization schedule, TEAEs will be associated with the most recent study product received.

The following summary tables and listings will be presented by study product group.

- Table of TEAEs by SOC and PT (Table 14.3.1.1).
- Table of TEAEs by Oral/Non-Oral and PT (Table 14.3.1.2)
- Table of treatment related TEAEs by SOC and PT (Table 14.3.1.3)
- Table of treatment related TEAEs by Oral/Non-Oral and PT (Table 14.3.1.4)
- Table of AEs related to COVID-19 by SOC and PT (Table 14.3.1.5).
- Listing of all AEs (Listing 16.2.7.1 for all randomized subjects; Listing 16.2.7.2 for non-randomized subjects)
- Listing of all AEs related to COVID-19 subject (Listing 16.2.7.3 for all screened subjects)
- Listing of deaths (Listing 14.3.2.1)
- Listing of non-fatal SAEs (Listing 14.3.2.2)
- Listing of TEAEs leading to study or product discontinuation (Listing 14.3.2.3)
- Listing of TEAEs classified as Oral (Listing 14.3.2.4)

In the event that there is nothing to report, a null table or listing will be produced.

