# 10.3 Time Period and Frequency for Collecting AE and SAE Information

All AEs, and therefore all SAEs, will be collected immediately after a subject provides consent to participate in the study by the completion (signature) of the ICF and until 5 days following last administration of the study product (or last study procedure).

Medical occurrences that began before obtaining informed consent will be recorded in the Medical History/Current Medical Conditions section of the eCRF, not the AE section.

Details recorded by the subject on a diary or similar document that meet the definition of an AE must also be discussed with the subjects and transcribed in the AE section of the eCRF.

All SAEs will be recorded and reported to the sponsor or designee immediately and under no circumstance should this exceed 24 hours. The investigator will submit any updated SAE data to the sponsor within 24 hours of it being available.

Investigators are not obligated to actively seek AEs or SAEs after the conclusion of the study participation. However, if the investigator learns of any SAE, including a death, at any time after a subject has been discharged from the study, and they consider the event to be reasonably related to the study product or study participation, the investigator must promptly notify the sponsor.

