## 10.6 Follow-up of AEs and SAEs

After the initial AE/SAE report, the investigator is required to proactively follow up with each subject and provide further information on the subject's condition.

All AEs (serious and non-serious) will be followed until resolution, until the condition stabilises, until the event is otherwise explained, or until the subject is lost to follow-up.

The investigator is obligated to perform or arrange for the conduct of supplemental measurements and/or evaluations as may be indicated or as requested by the sponsor to elucidate as fully as possible the nature and/or causality of the AE. This may include additional laboratory tests or investigations, histopathological examinations, or consultation with other health care professionals.

New or updated information will be recorded on the AE eCRF screen and on the paper SAE form (subject to the classification of the AE).

The investigator will submit any updated SAE data to the sponsor within 24 hours of receipt of the information.

Investigators are not obliged to actively seek AEs in former subjects. However, if the investigator learns of a SAE, including death, at any time after a subject has been discharged from the study, and considers the event reasonably related to the study product or study participation, the investigator will promptly notify the sponsor by emailing the information to the Case Management Group mailbox **PPD** with copy to the

Property of GSK Consumer Healthcare - Confidential

May not be used, divulged, published or otherwise disclosed without the consent of GSKCH

Clinical Protocol Template v9.0

Page 54 of 73

appropriate sponsor Study Manager.

The investigator will submit any updated SAE data to the sponsor within the designated reporting time frames.

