#### 12.3.3 Safety Analyses

Safety analyses will be performed on the Safety population, according to study product received. AEs will be regarded as 'treatment emergent' if they occur on or after the first study product use at Baseline (Visit 1). In case of misallocation, compared to the randomisation schedule, TEAEs will be associated with the most recent study product received.

Each AE will be categorized as oral or non-oral by the investigator, or medically qualified designee. All will be reviewed by the CRS prior to database lock and unblinding, and coded using the MedDRA.

A listing of all AEs will be presented for all subjects in the Safety population with the following AEs summaries (number of distinct AEs and frequency/proportion of subjects affected) will be presented by product group and overall:

Property of GSK Consumer Healthcare - Confidential

May not be used, divulged, published or otherwise disclosed without the consent of GSKCH

Clinical Protocol Template v9.0

Page 60 of 73

- Treatment emergent AEs
- Treatment emergent AEs by System Organ Class (SOC) and Preferred Term (PT)
- Treatment emergent AEs by Oral/Non-Oral and PT
- Treatment emergent treatment related AEs by Oral/Non-Oral and PT
- Treatment emergent treatment related serious AEs by SOC and PT

Separate listings will be presented for:

- Deaths, SAEs and any AEs leading to product or study discontinuation.
- OST findings (with a summary of abnormalities by visit)
- OHT findings (with a summary of changes by visit)
- Exposure to study product Section 12.3.5.1.

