#### Table 1-2 Study Objectives and Endpoints

Objectives	Endpoints		
Primary Objective	Primary Endpoint		
To determine the clinical efficacy of a 0.454% w/w SnF 2 toothpaste in reducing DH to an evaporative (air) stimulus (as measured by	Change from Baseline in Schiff sensitivity score at Week 12.		
GlaxoSmithKline Consumer Healthcare Confidential			

GlaxoSimunKime Consumer Healthcare Confidential

Statistical Analysis Plan Template v6.0

Page 9 of 36

Objectives	Endpoints
Schiff sensitivity score), compared to a	
negative control toothpaste, after 12 weeks	
twice daily use.	
Secondary Objectives	Secondary Endpoints
Efficacy	
To determine the clinical efficacy of a 0.454% w/w SnF 2 toothpaste in reducing DH to a tactile stimulus (as measured by tactile threshold), compared to a negative control toothpaste, after 12 weeks twice daily use.	Change from Baseline in tactile threshold (grams [g]) at Week 12.
To determine the clinical efficacy of a 0.454% w/w SnF 2 toothpaste in reducing DH to an evaporative (air) stimulus (as measured by Visual Analogue Scale [VAS]), compared to a negative control toothpaste, after 12 weeks twice daily use.	Change from Baseline in VAS (millimeters [mm]) at Week 12.
To determine the clinical efficacy of a 0.454% w/w SnF 2 toothpaste in reducing DH to evaporative (air) and tactile stimuli (as measured by Schiff sensitivity score/VAS and tactile threshold, respectively), compared to a negative control toothpaste, after 6 weeks twice daily use.	Change from Baseline in Schiff sensitivity score, tactile threshold (g) and VAS (mm) at Week 6.
To determine the clinical efficacy of a 5.0% w/w calcium sodium phosphosilicate (CSPS) toothpaste (positive control) in reducing DH to evaporative (air) and tactile stimuli (as measured by Schiff sensitivity score/VAS and tactile threshold, respectively), compared to a negative control toothpaste, after 6 and 12 weeks twice daily use.	Change from Baseline in Schiff sensitivity score and tactile threshold (g) and VAS (mm) at Week 6 and Week 12.
Safety	
To evaluate the safety and oral tolerability of the study toothpastes when used twice daily for 12 weeks.	Treatment emergent adverse events (TEAEs)

This study will be considered successful if there is a statistically significant difference between 0.454% SnF2 and negative control by the primary efficacy variable, change from Baseline in Schiff sensitivity score at week 12.

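### The TEAE definition has no clause for worsening, so an adverse event that starts in acclimatisation and worsens on study toothpaste can miss the safety endpoint; separately, the SAP narrows the protocol's discontinuation listing without declaring it

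*SAP*

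**What the plan says.** The safety objective, in SAP Table 1-2 as in protocol Table 3-1, has a single endpoint: "Treatment emergent adverse events (TEAEs").

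Collection starts before study product. Protocol 10.3 states: "All AEs, and therefore all SAEs, will be collected immediately after a subject provides consent". Screening takes place 14-28 days before randomisation (protocol 8.1), and subjects brush with the acclimatisation toothpaste in between.

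SAP 4.5.1 defines the endpoint: "Treatment emergent adverse events (TEAEs) are defined as new AEs that occur on or after the first study product use at Baseline" (Visit 2). It then closes off earlier events: "AEs with an onset date/time prior to the first study product usage will be considered as non-treatment emergent". Protocol 12.3.3 uses the same cut-off and is also silent on worsening: "AEs will be regarded as 'treatment emergent' if they occur on or after the first study product use at Baseline (Visit 1"). The visit number there is a slip, since Baseline is Visit 2 everywhere else.

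On an event already on file, protocol 10.6 says: "New or updated information will be recorded on the AE eCRF screen".

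For discontinuations, protocol 12.3.3 asks for a listing of "Deaths, SAEs and any AEs leading to product or study discontinuation". The SAP provides "Listing of TEAEs leading to study or product discontinuation (Listing 14.3.2.3"), and the title in SAP Appendix 1 carries the same restriction.

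**The concern.** Oral tolerability is part of the safety objective, and a mild oral irritation that becomes moderate or severe on the assigned paste is one way poor tolerability shows itself. The acclimatisation paste and the negative control are the same named product (protocol Tables 6-1 and 6-2). Only the test and positive-control arms therefore change paste at Baseline, and aggravation after that change is of direct interest.

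Under a rule based on onset date alone, such an aggravation can be related to the product and lead to stopping it, and still add nothing to the by-arm summaries of the only safety endpoint. The discontinuation listing is where a reader would look next, and it carries the same TEAE filter although the protocol asked for it without one.

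**Working it through.** No sample size, power or significance level is involved, so the check sets the provisions side by side and follows one event through the displays.

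**Step 1: can an event begin before the cut-off?** Yes. Collection runs from consent, the AE definition in protocol 10.1 covers lead-in products, and an oral soft tissue (OST) examination takes place at Baseline before the first supervised brushing with study toothpaste (protocol 8.2.1.4 and 8.2.1.8). An irritation first seen there, or noted in the diary, has its onset before first use.

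**Step 2: how would worsening be recorded?** Three provisions bear on this.
- Protocol 10.1 makes exacerbation of a chronic or intermittent pre-existing condition an AE.
- Protocol 9.3.1 and 9.3.2 record an OST or oral hard tissue (OHT) finding that worsens from Screening as an AE.
- Protocol 10.6 sends new information on a reported AE to the AE screen.

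None of them says whether an AE already opened during acclimatisation, and worse at Week 6, is updated under its old onset date or entered again with a new one. Both routes are open.

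**Step 3: where does the event appear?** Take a randomised subject with a non-serious oral AE, mild in acclimatisation and severe on study toothpaste, that leads to stopping the product.

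| SAP display | Existing record updated | New record, onset on product |
|---|---|---|
| Tables 14.3.1.1, 14.3.1.2 (TEAEs) | absent | present |
| Tables 14.3.1.3, 14.3.1.4 (related TEAEs) | absent | present if judged related |
| Listing 14.3.2.4 (oral TEAEs) | absent | present |
| Listing 14.3.2.3 (TEAEs leading to discontinuation) | absent | present |
| Listing 16.2.7.1 (all AEs) | present | present |
| Table 14.1.1, Listing 16.2.1.1 (disposition) | present if the subject leaves the study | same |
| Table 14.3.4.1, Listings 16.2.8.1.1 and 16.2.8.1.2 (OST) | present if visible on examination | same |

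Table 14.3.4.1 counts subjects with and without abnormalities at each visit, so worsening of an abnormality already present leaves its counts unchanged. If the event were fatal or serious it would also be in Listing 14.3.2.1 or 14.3.2.2, neither of which is restricted to TEAEs.

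**Step 4: the discontinuation listing on its own.** This part needs no worsening. A randomised subject who stops because an acclimatisation AE persists unchanged belongs in the listing as protocol 12.3.3 describes it, and is not in Listing 14.3.2.3. SAP section 5 says changes from the protocol's analysis are set out in Table 5-1. Its single entry concerns the population for the all-AE listing.

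**Step 5: scale.** The share of the AE collection window that lies before the cut-off is a / (a + d + 5), where a is the acclimatisation period (14 to 28 days), d is the time from Day 1 to Week 12 (84 ± 4 days), and 5 is the days of follow-up after last use.
- Nominal visits: 14/(14 + 84 + 5) = 14/103 = 13.6%, to 28/(28 + 84 + 5) = 28/117 = 23.9%.
- Extremes of the visit window: 14/(14 + 88 + 5) = 14/107 = 13.1%, to 28/(28 + 80 + 5) = 28/113 = 24.8%.

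This is a share of time. The documents give no AE rate, so it cannot be turned into a number of events.

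**The case against.** The strongest reply is that exclusion depends on how the site records worsening, and the documents do not settle that. If worsening is entered as its own AE, it meets the SAP's definition as it stands. The protocol also treats worsening as reportable in several places: the exacerbation clause in 10.1 and the OST and OHT rules in 9.3. This stands. A reader might infer that an acclimatisation AE can never become treatment-emergent whatever happens to it, and the text does not support that. What remains is narrower: a further worsening of an AE already on file, for which no recording rule exists.

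A second reply is that the SAP follows the protocol here. That also stands for the definition, since protocol 12.3.3 has no worsening clause either. The gap belongs to both documents and is not a departure by the SAP. It does not stand for Listing 14.3.2.3, where the SAP is narrower than the protocol and does not say so.

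A third is that nothing is hidden. A reader might infer that these events vanish from the report or survive only in the all-AE listing. Step 3 shows otherwise. Still, a line listing or a disposition count does not replace the by-arm summary of the safety endpoint.

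Finally, the practical reach is small. These are marketed toothpastes, safety is described without formal testing, subjects must be in good oral health and are checked again at Baseline, and study success rests on the Schiff score alone. All of this is fair and limits the weight of the point.

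**Conclusion.** The point holds in two parts of different certainty.

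- **Listing 14.3.2.3.** It contradicts protocol 12.3.3 and the change is undeclared. This rests on the text alone. It affects only randomised subjects who stop because of an AE that began before first use.
- **TEAE definition.** It allows on-product aggravation to be left out of the TEAE tables and the oral TEAE listing. This rests on one assumption, that the site updates the existing record. The documents leave that open, and this is itself the gap.

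The size is unknown. The 13% to 25% in Step 5 might be read as the proportion of AEs lost, but it is only calendar time. An affected event must start in acclimatisation, still be present at Baseline, worsen on product and keep its old onset date. Nor can it be said that the omission favours any arm: the paste change at Baseline makes that possible, but nothing in the documents measures it.

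The efficacy conclusions are untouched. The change is still worth making before unblinding, because a stated rule can remove relevant events from the only safety endpoint and the correction is almost free.

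**What to change.** 1. In SAP 4.5.1, aligned with protocol 12.3.3, define a TEAE as an AE with onset on or after first study product use, or an AE with earlier onset that increases in intensity or becomes serious on or after first use. Correct the Baseline visit number in protocol 12.3.3 at the same time.
2. State, in the protocol's AE section or the eCRF completion instructions, that such worsening is entered as a new AE record with its own onset date.
3. Change Listing 14.3.2.3, in SAP 4.5.1 and Appendix 1, to all AEs leading to study or product discontinuation. If the sponsor prefers to keep the TEAE restriction, declare and justify it in Table 5-1.
4. Enter the revised TEAE definition in Table 5-1 if the protocol is not amended.

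The cost is a few sentences, one site instruction and one listing filter. TEAE counts may rise slightly. Sample size, efficacy analyses and study conduct are otherwise unaffected.

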## 4.5.2 Other Safety Variables

Other safety variables are listed below:

• OST examination

GlaxoSmithKline Consumer Healthcare Confidential Statistical Analysis Plan Template v6.0 Page 25 of 36

#### • OHT examination

#### 4.5.2.1 OST Examination

The OST examination will be accomplished by direct observation and palpation, using retraction aids as appropriate, and will include examination of the labial mucosa (including lips), buccal mucosa, mucogingival folds, gingival mucosa, hard palate, soft palate, tonsillar area, pharyngeal area, tongue, sublingual area, submandibular area, and salivary glands. The results of the examination will be recorded in the eCRF as either 'normal' or 'abnormal', with details of any abnormalities.

Any observation that changes from 'normal' to 'abnormal', or worsens, from the OST examination completed at Screening will be recorded as an AE.

OST will be summarized (number of subjects and percentages with abnormalities, without abnormalities, or OST not examined) by visit and study product in Table 14.3.4.1 for all subjects in the Safety Population. OST examination will be listed (Listing 16.2.8.1.1) with all records ('normal', 'abnormal' and 'not examined') for all randomized subjects, and a separate listing will be presented for 'abnormal' records only (Listing 16.2.8.1.2) for all randomized subjects.

#### 4.5.2.2 OHT Examination

The OHT examination will be accomplished by direct observation, using retraction aids as appropriate, and will identify enamel irregularities, tooth fractures, grossly carious lesions/gross decay, defective/faulty restorations (all direct & indirect restorations including fixed/removal prostheses), non-carious tooth surface loss (abrasion, attrition, abfraction and erosion), any other hard tissue irregularities (e.g., hypo/hypermineralisation, decalcification) and significant tooth staining. Observations will be listed as 'absent' or 'present'; conditions noted as 'present' will be described in the eCRF. Any observation that changes from 'absent' to 'present', or worsens, from the OHT examination completed at Screening will be recorded as an AE.

The presence of any implants, fixed or removable dentures, fixed or removable orthodontic braces/bands, fixed orthodontic retainers, full crowns or veneers will be recorded, along with evidence of gross intra-oral neglect or the need for extensive dental therapy.

The OHT examination is also used to assess the dentition against the general and specific dentition exclusions.

OHT will be summarized (number of subjects and percentages of 'Absent', 'Present' or 'OST not examined') by visit and study product in Table 14.3.4.2 for all subjects in the Safety Population. OHT examination will be listed (Listing 16.2.8.2) for all randomized subjects.

## 4.6 Analysis of Other Variables

Not applicable.

GlaxoSmithKline Consumer Healthcare Confidential Statistical Analysis Plan Template v6.0 Page **26** of **36** 

